### **Exclusion Criteria:**

- Revision surgery
- Pediatric patients
- Patients with Cervical vertebra fracture(s)
- Patients with Cervical Spine Tumors
- Patients with active infection
- Patients with a known allergy to Depo-Medrol
- Patients who refuse to participate
- Non English speakers

Age Range:

>18 years

## Target Enrollment:

128

#### Interventions and Observations:

We plan to observe the effect on SWAL-QOL scores in patients following ACDF in groups that either receive or do not receive intraoperative topical steroid. All individuals undergoing 2-4 level ACDF that meet the inclusion criteria will be randomized to either: 1) treatment arm or 2) control arm. Both arms will undergo their planned surgeries and will receive the exact same procedure and standard of care as if they were not enrolled in a study. The only difference is that the treatment arm will receive 40 mg of Depo-Medrol delivered with one SURGIFLO Hemostatic Matrix Kit (Ethicon, Somerville, NJ, USA) injectable delivery vehicle prior to closure in the prevertebral soft tissues. The control group will receive only SURGIFLO Hemostatic Matrix Kit prior to closure. The surgeon will inject the material directly in the pre-vertebral soft tissue.

Both groups will have the same standard evaluations both pre-operatively and post operatively. The SWAL-QOL questionnaire will be utilized as the primary instrument to measure outcome. Other questionnaires, the EAT-10 and Bazaz Dysphagia Score, which grades will be used to assess dysphagia and swallowing difficulty. Additionally, the Neck Disability Index and the Visual Analog Scale for neck and arm pain will be administered to assess how neck related pain impacts the patients' quality of life. The EAT-10, Bazaz, and Visual Analog scale will be utilized to assess secondary outcomes. These questionnaire will be given to the patients to complete pre-operatively, on post-operative day one, post-operative day two, at post-operative week 4-6, post-operative month 3, post-operative month 6, and post-operative month 12. The Neck Disability Index will be completed pre-operatively, at post-operative week 4-6, post-operative month 12.

All test or images are standard of care. Administration of the EAT-10, SWAL-QOL survey, Neck Disability Index, VAS (Neck and Arm Pain), and Bazaz Dysphagia Score are not standard of care. Funds are not required for administration of these questionnaires.

#### Randomization:

The randomization will be done prior to surgery.

The randomization protocol will be stratified by procedure to ensure proper distribution of cases in the study. This will also ensure equivalent numbers of patients in each group over the course of the study in case early stopping is required as well as randomize any procedure effect that may contribute to the results. Randomization will be concealed using sealed opaque envelopes containing the randomization assignment for each enrolled patient. Randomization assignment will be made known only to the unblinded research assistant.

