#### Outcomes:

To determine if topical steroids placed intraoperatively in the wound of an anterior cervical discectomy and fusion surgery reduce the incidence of postoperative swallowing difficulty using the SWAL-QOL outcome measure. SWAL-QOL will be administered pre-operatively, on post-operative day one, post-operative day two, post-operative 4-6 weeks, post-operative 3 months, post-operative 6 months, and post-operative 12 months. Differences in SWAL-QOL scores will be stratified based on levels fused (2-, 3-, and 4-levels).

The Bazaz Dysphagia Score and the Eating assessment Tool 10 (EAT-10) will be administered at the same time points to provide additional data about swallowing difficulty

Additionally, questionnaires that assess how neck and arm related pain affects the patient's quality of life will be administered pre-operatively (NDI & VAS), post-operatively day 1 and 2 (VAS), week 4-6 (NDI & VAS), month 3 (NDI & VAS), month 6 (NDI & VAS), and at month 12 (NDI & VAS).

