### Background:

Swallowing difficulties are a major side effect of anterior neck fusion surgery. Steroids have the effect of reducing inflammation and swelling, factors considered likely to cause swallowing difficulties following anterior neck surgery. This study looks to determine if steroids placed into the wound at the end of an anterior neck fusion surgery decrease the severity of a patient having swallowing difficulty following the surgery.

Dysphagia is a serious post-operative concern in patients following anterior cervical surgery. Although many authors have acknowledged that dysphagia is often incompletely understood and defined, there is a significant amount of literature to support the significance of this clinical entity. Lee et al (The Spine Journal 2007) found the incidence of post-operative dysphagia at 1, 2, 6, and 12 months post-operatively to be 54.2%, 33.6%, 18.6%, 15.2%, and 13.6%, respectively. Rihn et al (CORR 2011) found the

incidence to be 71% at two weeks post-operatively. Bazaz et al (Spine 2002), found it to be 50.2%, 32.2%, 17.8%, and 12.5% at 1, 2 6, and 12 months post-operatively. Moreover, Lee et al (Spine 2010) performed a systematic review and found in 17 studies the average incidence of dysphagia to be 13-21% at one-year post-operatively.

This study will utilize a validated questionnaire, SWAL-QOL, to evaluate swallowing difficulty and dysphagia. In addition, the study will investigate these outcomes in 2-4 level ACDFs, which have not been examined previously.

If topical steroid use can be proven to be safe and effective, it is a relatively inexpensive, easy measure to institute to diminish the occurrence of a serious complication following anterior cervical surgery and improve patient-reported outcomes.

This is a randomized, prospective clinical trial.

Study Drug:

Depo-Medrol (Methylprednisolone acetate)

This drug is FDA-approved and being utilized in an "off-label" manner. We confirmed with clinical research administration that the use of this drug does not require notification to the FDA or filing of an IND.

Inclusion Criteria:

Any patient > 18 years undergoing a 2-4 level anterior cervical discectomy and fusion

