# **Statistical Plan:**

Steroid and Control arms were compared in terms of demographics and surgical information using a student's independent t-test and chi square/fisher exact test for normally distributed data, and a Mann-Whitney U test otherwise. In terms of PROs, a Mann-Whitney U test was performed to compare the group medians for dysphagia scores at Baseline, Post-op Day 1, Post-op Day 2, post-operative week 4-6, post-operative month 3, post-operative month 6, and post-operative month 12. In addition, a pre-post op comparison was conducted by calculating the change in PRO from baseline to each post-operative time point for each patient. Statistical significance was determined for all results with p<0.05.

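### Randomisation is stratified by procedure, but the Mann-Whitney comparison ignores the strata: a modest, conditional loss of power, not a validity error

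*Combined protocol and SAP*

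**What the plan says.** Three sections bear on this.

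- **Randomization.** "The randomization protocol will be stratified by procedure to ensure proper distribution of cases in the study". One stated purpose is to "as well as randomize any procedure effect that may contribute to the results"; another is to "ensure equivalent numbers of patients in each group over the course of the study". The timing is fixed: "The randomization will be done prior to surgery". The section does not say what the procedure categories are, how many there are, or whether blocks are used within them.
- **Statistical Plan.** At each visit, "a Mann-Whitney U test was performed to compare the group medians for dysphagia scores". Changes from baseline are also to be calculated for each patient. No stratified test, stratum covariate or level-specific analysis appears.
- **Outcomes.** "Differences in SWAL-QOL scores will be stratified based on levels fused (2-, 3-, and 4-levels". No method is attached, and the Statistical Plan does not return to it.

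The inclusion criterion admits patients "undergoing a 2-4 level anterior cervical discectomy and fusion", and the Background gives as its novelty that "the study will investigate these outcomes in 2-4 level ACDFs, which have not been examined previously".

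**The concern.** A factor is normally used to stratify randomisation because it is expected to predict the outcome, and the protocol says as much. If the analysis then ignores that factor, the between-stratum variation stays in the noise against which the treatment effect is judged. The design pays for the stratification and the test does not collect the benefit.

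Two ambiguities add to this. First, *procedure* is undefined. Every patient has the same operation, differing in the number of levels, so planned level count is the natural reading, but no section says so. Second, randomisation takes place before surgery, so a level stratum could only be *planned* levels, whereas the Outcomes section refers to levels *fused*. The two can differ for a patient whose operation changes.

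At stake is some power in a trial of 128 patients, and clarity about which factor the analysis should carry.

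**Working it through.** **What can be reproduced.** Target enrollment is 128, with no effect size, SD, power or dropout beside it, so there is no power figure in the plan to reproduce.

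**Inputs from the documents.** 128 patients, and significance at p<0.05. Equal group sizes are implied by the Randomization section, which gives 128/2 = 64 per arm.

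**Inputs assumed.** Two-sided testing; three level strata of 32/22/10 patients per arm (22/21/21 as a check); a linear level effect; normal outcomes; strata explaining R² = 5, 10 or 20% of variance; treatment effect d from 0.3 to 0.8 within-stratum SD. With the 32/22/10 mix, these R² values correspond to 0.31, 0.45 and 0.68 SD per added level, so 20% is a strong effect.

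**Approximation with arms balanced within strata.** Let s = (d / total SD) × √(64/2) × √(3/π), where total SD = 1/√(1−R²).

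- Mann-Whitney power ≈ Φ((s − 1.96)/√(1−R²))
- Stratified rank test power ≈ Φ(s/√(1−R²) − 1.96)
- Mann-Whitney size ≈ 2Φ(−1.96/√(1−R²))

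For d = 0.5 and R² = 10%, total SD = 1/√0.9 = 1.054, so s = (0.5/1.054) × 5.657 × 0.977 = 2.62.

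- Mann-Whitney: Φ((2.62 − 1.96)/0.949) = Φ(0.70) = 75.7%
- Stratified: Φ(2.62/0.949 − 1.96) = Φ(0.80) = 78.9%
- Difference: 3.2 points

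The size formula gives 4.4, 3.9 and 2.8% at R² = 5, 10 and 20%, so the test is conservative here.

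**Simulation, 32/22/10 per arm, balanced within strata** (20,000 to 40,000 trials per cell; the 0.8 SD row uses the approximation). Power in %, Mann-Whitney v van Elteren:

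| Effect (within-stratum SD) | R² 5% | R² 10% | R² 20% |
|---|---|---|---|
| 0.3 | 35.9 v 37.4 | 33.6 v 37.1 | 28.5 v 36.7 |
| 0.4 | 57.2 v 58.6 | 54.7 v 58.4 | 49.2 v 58.2 |
| 0.5 | 76.6 v 77.7 | 74.5 v 77.6 | 70.4 v 77.7 |
| 0.6 | 89.7 v 90.2 | 88.5 v 90.1 | 85.7 v 90.2 |
| 0.8 | 99.2 v 99.3 | 99.1 v 99.3 | 98.7 v 99.3 |

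The gains are about 1.5/3.5/8 points at 0.3 SD, 1.5/3.7/9 at 0.4, 1/3/7 at 0.5, 0.5/1.6/4.5 at 0.6, and 0.1/0.2/0.6 at 0.8. At 0.5 SD, Mann-Whitney would need about 132, 136 or 150 patients instead of 128 to match, that is, 4, 8 or 22 more.

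**Size.** With balance, simulated Mann-Whitney size is 4.6, 3.8 and 2.9% at R² = 5, 10 and 20%; van Elteren stays at 5.0 to 5.1%. Without within-stratum balance, Mann-Whitney size is 4.9, 5.1 and 5.0%.

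**Sensitivity at 0.5 SD**, gain at R² = 5/10/20%:

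- Strata 22/21/21: 1.0/3.1/7.6 points.
- Without within-stratum balance: 75.6 v 76.6, 73.6 v 76.7 and 68.6 v 76.9%, or 1.0/3.1/8.3.
- Tied scores with about 28% at the ceiling: 72.5 v 73.5, 70.0 v 72.9 and 64.7 v 72.4%, or 1.0/2.9/7.7.
- 20% missing (26/18/8 per arm): 67.4 v 68.6, 65.0 v 68.0 and 60.5 v 68.3%, or 1.2/3.0/7.8.
- Effect set at 0.5 *total* SD: about 1/2.5/5.4.

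**When the strata predict little.** At R² = 0 the van Elteren test loses 0.3 to 0.7 points with balance and 0.7 to 1.3 without. At R² = 2% the difference runs from −0.5 to +0.4. Break-even lies at about 2 to 4%.

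**The case against.** The strongest reply is that the gain rests wholly on quantities the documents do not give. No section says how strongly level count, or any other procedure factor, predicts SWAL-QOL. At 5% of variance the gain is worth about four patients; only the 20% case is material, and that assumes a strong effect. If the true treatment effect is large, almost nothing is lost. All of this stands, and it is why the point is minor.

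It can also be said that, if *procedure* means level count, the factor is not wholly absent from the plan, because the Outcomes section promises stratification by level. That is fair as far as it goes. But the promise has no method, is not carried into the Statistical Plan, and refers to fused rather than randomised levels. If *procedure* means something else, the principle still applies, but the three-level figures above need not.

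Van Elteren is also one choice among several; a stratum-adjusted model would serve too. It is proposed here because it is the closest change to the rank test already planned.

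A reader might infer that ignoring the strata makes the planned test invalid. It does not: size is at or below about 5% in every setting examined. A reader might also take the Outcomes sentence as separate significance tests per level. The documents do not say that, and nothing here relies on it.

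**Conclusion.** The mismatch is real and visible in the text: the design stratifies by a factor judged capable of affecting the results, and the planned test leaves that factor out. The consequence is a modest loss of efficiency. The Mann-Whitney test remains valid. It is conservative when the stratum is prognostic and the arms are balanced within strata, whatever the factor is; without that balance its size is about 5%. Because no block method is described, within-stratum balance is not assured.

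The gain of 1, 3 or 7 points should not be read as a property of this trial. It holds for 0.5 within-stratum SD, 64 per arm and three level strata explaining 5, 10 or 20% of variance, and it shrinks as the effect grows. Nor should level count be taken as the established meaning of *procedure*; that is an inference. Minor severity.

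**What to change.** **Statistical Plan.** Replace the between-arm Mann-Whitney test on dysphagia scores with wording such as: *The arms will be compared on SWAL-QOL, EAT-10 and Bazaz scores at each time point, and on their changes from baseline, with a van Elteren (stratified Wilcoxon) test using the stratum recorded at randomization. A stratum with no patients in one arm at a time point will be pooled with another stratum by a rule fixed in advance.* State the pooling rule once the factor is named; it must also work if the categories have no natural order.

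**Randomization.** Name the factor and list its categories, for example planned number of levels (2, 3 or 4) if that is what is meant. If it is something else, use that factor in the test.

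**Outcomes.** Align the level sentence with the named factor: planned levels as randomised, if level count is meant.

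**Cost.** Wording in three sections and no new data. If level count is the factor, the planned number must already be known before surgery to apply the inclusion criterion, so it can be recorded at randomisation. If the stratum turns out not to be prognostic, the price is about 0.3 to 0.7 points of power with within-stratum balance and up to about 1.3 without, for three strata of the sizes assumed.

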# **Statistical Plan:**

Steroid and Control arms were compared in terms of demographics and surgical information using a student's independent t-test and chi square/fisher exact test for normally distributed data, and a Mann-Whitney U test otherwise. In terms of PROs, a Mann-Whitney U test was performed to compare the group medians for dysphagia scores at Baseline, Post-op Day 1, Post-op Day 2, post-operative week 4-6, post-operative month 3, post-operative month 6, and post-operative month 12. In addition, a pre-post op comparison was conducted by calculating the change in PRO from baseline to each post-operative time point for each patient. Statistical significance was determined for all results with p<0.05.

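### The between-arm SWAL-QOL analysis is a set of unadjusted visit-by-visit Mann-Whitney tests, with no baseline adjustment, effect estimate or missing-data method; a baseline-adjusted repeated-measures model uses the same data better

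*Combined protocol and SAP*

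**What the plan says.** SWAL-QOL is the lead outcome: "The SWAL-QOL questionnaire will be utilized as the primary instrument to measure outcome" (Interventions and Observations). It is collected before surgery and six times afterwards, the last three being "post-operative 3 months, post-operative 6 months, and post-operative 12 months" (Outcomes). No visit is named as primary.

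Under Statistical Plan, "a Mann-Whitney U test was performed to compare the group medians for dysphagia scores at Baseline, Post-op Day 1, Post-op Day 2", and the list continues with "post-operative week 4-6, post-operative month 3, post-operative month 6, and post-operative month 12. In addition, a pre-post op comparison". Baseline enters only through that second comparison, made by "calculating the change in PRO from baseline to each post-operative time point for each patient"; no test or model is named for it. The threshold is the same throughout: "Statistical significance was determined for all results with p<0.05".

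Two design features do not reach the analysis. Under Randomization, "The randomization protocol will be stratified by procedure to ensure proper distribution of cases in the study". Under Outcomes, "Differences in SWAL-QOL scores will be stratified based on levels fused (2-, 3-, and 4-levels". The Statistical Plan mentions neither. It also gives no analysis population, missing-data rule, attrition allowance, effect estimate or confidence interval.

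**The concern.** A Mann-Whitney test needs an observed score, and no imputation is described. By default, then, each visit's test uses only the patients who have a score at that visit. The documents do not say this in words; it follows from the method.

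Three things are lost. First, a baseline SWAL-QOL score is collected but not used as a covariate, although it should explain part of the variation in later scores. Second, a patient with no month-12 score contributes nothing to the month-12 comparison, whatever earlier scores are held. Third, the reader gets p-values without the size of the benefit or its uncertainty. In addition, the Mann-Whitney test does not in general compare medians, as the plan says it does; it is sensitive to any tendency for one arm to score higher than the other.

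At stake is the chance of detecting a real benefit in a trial of 128 patients and, at later visits, some attenuation of the estimated effect if swallowing influences who stays in follow-up.

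**Working it through.** **Inputs from the documents.** Target Enrollment gives 128 patients. The significance threshold is 0.05. There is one baseline and six post-operative assessments.

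**Assumptions, because the documents give no figures.** 64 per arm, two-sided testing, between-visit correlation ρ of 0.5 (range 0.3-0.7), effects of 0.35 or 0.5 SD, and the dropout patterns below.

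**The plan's own figure.** The target of 128 comes with no power inputs, so it cannot be reproduced. A 0.5 SD effect at 80% power needs 2 × (1.960 + 0.842)² / 0.5² = 62.8, so 63 per arm or 126 in total; the exact t-test gives 128. That may be coincidence and is not taken as the plan's basis.

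**Step 1: value of baseline, complete data, one visit.** In SD units the standard error is √(2/64) = 0.1768 unadjusted and √((1 − ρ²) × 2/64) with baseline as covariate. Power is Φ(δ/SE − 1.96).

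| δ = 0.35 SD | SE | Power |
|---|---|---|
| Unadjusted | 0.1768 | 51% |
| Baseline-adjusted, ρ = 0.3 | 0.1686 | 55% |
| Baseline-adjusted, ρ = 0.5 | 0.1531 | 63% |
| Baseline-adjusted, ρ = 0.7 | 0.1262 | 79% |

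For δ = 0.5 SD and ρ = 0.5, the same formula gives Φ(2.828 − 1.96) = 81% unadjusted and Φ(3.266 − 1.96) = 90% adjusted.

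**Step 2: adding missing data.** Simulation with 1,500 trials per scenario: normal scores, correlation 0.5 between all visits, a 0.5 SD effect at every post-operative visit, and permanent dropout from week 4-6 onward. The log-odds of dropout have intercept logit(0.05) and change by 1.2 per SD of the previous score, in the same way in both arms.

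| | Week 4-6 | Month 12 |
|---|---|---|
| Missing | 7-11% | about 23% |
| Available-case mean difference | 0.47-0.48 SD | 0.44-0.45 SD |
| Power, Mann-Whitney | 69-72% | about 59% |
| Power, available-case baseline adjustment | 82-86% | about 78% |
| Power, mixed model | – | about 84% (estimate 0.50 SD) |

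The Monte Carlo standard error is about √(0.59 × 0.41 / 1500) = 1.3 percentage points. At month 12 the total gain is 84 − 59 = 25 points, of which 78 − 59 = 19 come from simple baseline adjustment. The joint model adds about 6 points and removes the remaining attenuation.

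**Step 3: false positives with no true effect.** With the same dropout mechanism in both arms, Mann-Whitney at month 12 rejects 4.5-4.9% of the time. With dropout related to score in opposite directions by arm, it rejects about 31-34% at month 12 but only about 7% at week 4-6; the mixed model stays near 5% at month 12. A variant with an early effect that has vanished by month 12 gave 43%.

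**Step 4: limits of the model.** A separate simulation made only month 12 missing (20-30%, ρ of 0.5-0.7), with opposite directions by arm.
- Missingness driven by the observed month-6 score: Mann-Whitney rejects 14-39%, the model 4-5%.
- Missingness driven by the unseen month-12 score: available-case bias is −0.34 to −0.51 SD. The model's bias is smaller but still −0.13 to −0.32 SD, and it rejects 18-42% when there is no effect.

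**The case against.** The case for the plan as written has four parts.

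**The tests are not invalid.** A reader might infer that they are valid only if missing forms are unrelated to swallowing. Step 3 shows otherwise: score-related dropout that works the same way in both arms leaves the level at 5% when there is no effect. Serious inflation needs a mechanism that differs by arm. Nothing in the documents suggests one, and the Randomization section restricts knowledge of the assignment to one unblinded assistant, which makes it less plausible. This part stands.

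**A mixed model is no cure for missing data.** A reader might infer that it removes the bias whenever swallowing affects follow-up. It does so only if data are missing at random and the model is correct (Step 4). This stands, and is why the fix includes a sensitivity analysis.

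**The repeated scores are not the main loss.** With complete data and no baseline covariate, an unstructured mixed model gives the same mean difference at a visit as a two-sample comparison. The gain comes mostly from baseline. This also stands. The change-from-baseline comparison does use baseline, but with no test named it does not fill the gap.

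**Rank tests suit bounded, skewed scores, and the simulations used normal ones.** This stands in part. In a run with scores capped at a ceiling (about 27% of controls and 46% of treated patients at the cap), the model estimated 0.31 against a true mean difference of 0.32, with about 4% type I error and 72% power; Mann-Whitney had 52%. That is one pattern only. Retained Mann-Whitney tests cannot check residuals, so a direct check is still needed.

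**Conclusion.** The concern holds as one of efficiency and reporting, with a smaller missing-data component. The planned tests leave out the baseline score, the randomisation stratum and levels fused, give no effect size, and misdescribe what Mann-Whitney compares.

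Under the assumed inputs, baseline adjustment alone is worth roughly 10 to 17 points of power at week 4-6 (82 − 72 to 86 − 69) and about 19 at month 12; the joint model takes the month-12 gain to about 25. Bias is small at week 4-6. At month 12 the available-case estimate falls short by about 0.05-0.06 SD of a true 0.5 SD.

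The documents do not support reading the 31-34% false-positive rate as expected behaviour: it is a worst case requiring opposite dropout patterns in the two arms. Attrition, correlation, SD and effect size are all assumed, and the size of the gain depends chiefly on how strongly baseline predicts later scores.

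**What to change.** For SWAL-QOL, replace the visit-wise tests as the main analysis with one mixed model for repeated measures:

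- **Population:** all randomised patients, in their assigned arm.
- **Terms:** arm, visit, arm-by-visit, baseline score, baseline-by-visit, and planned levels or procedure stratum (one term if these are the same thing), with unstructured covariance.
- **Reporting:** adjusted difference and 95% confidence interval at each post-operative visit.
- **Primary test:** name one primary visit. The model alone does not deal with six tests at 0.05, whose familywise error would be 1 − 0.95⁶ = 26.5% if independent and about 16-24% at correlations of 0.7 to 0.3.
- **Missing data:** state that the model assumes missing at random, and add a delta-adjusted sensitivity analysis for data not missing at random.
- **Model checks:** examine residuals, and specify a robust, bootstrap or ordinal alternative if ceiling effects are marked.
- **Mann-Whitney:** keep it as supportive only, and drop the statement that it compares medians.

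Do the same for EAT-10 and VAS. For NDI, first reconcile its visits: Outcomes includes months 3 and 6, while Interventions and Observations lists only the pre-operative, week 4-6 and month-12 assessments.

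The cost is revised wording and standard software, with no new data or visits. The downside is that the estimand becomes a mean difference and the model assumes roughly normal residuals for a bounded score.

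### Pre-operative SWAL-QOL is collected but no between-arm analysis adjusts for it, and the change-from-baseline comparison has no stated test, contrast or role

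*Combined protocol and SAP*

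**What the plan says.** The Interventions and Observations section sets the primary measure: "The SWAL-QOL questionnaire will be utilized as the primary instrument to measure outcome". The Outcomes section has it completed before surgery and at six visits afterwards ("SWAL-QOL will be administered pre-operatively, on post-operative day one, post-operative day two, post-operative 4-6 weeks, post-operative 3 months", then 6 and 12 months).

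For the comparison of arms, the Statistical Plan says that "a Mann-Whitney U test was performed to compare the group medians for dysphagia scores at Baseline, Post-op Day 1, Post-op Day 2", and continues through the later visits. No covariate is mentioned. It adds that "a pre-post op comparison was conducted by calculating the change in PRO from baseline to each post-operative time point for each patient", and closes with "Statistical significance was determined for all results with p<0.05".

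On the number of levels, the Outcomes section states: "Differences in SWAL-QOL scores will be stratified based on levels fused (2-, 3-, and 4-levels". The Randomization section states: "The randomization protocol will be stratified by procedure to ensure proper distribution of cases in the study". The Statistical Plan takes up neither. No ANCOVA, mixed model or other baseline-adjusted analysis appears anywhere in the document.

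**The concern.** The trial collects the most useful covariate for its primary measure, the patient's own pre-operative score, and makes poor use of it. The raw comparison ignores it. The change score subtracts it one-for-one whatever its correlation with the later score, which adds noise when that correlation is low. Testing the arms against each other at baseline does not adjust any later comparison.

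The role of the change score is also open. The text does not say whether change is compared between arms or described within them, by which test, or whether raw or change scores settle the question. Because the 0.05 threshold applies to every result, a reader cannot tell which analysis decides.

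At stake are power that costs nothing to recover, an estimate less exposed to chance baseline imbalance, and a clear statement of the deciding analysis.

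**Working it through.** **Inputs from the document.** Total enrolment is 128 (Target Enrollment), with no derivation. There are two arms with equal numbers intended (Randomization). The threshold is 0.05 (Statistical Plan). No power, effect size, SD, dropout or correlation is given, so the plan has no figure of its own to reproduce.

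**Assumptions.** 64 per arm, two-sided 0.05, a latent shift of 0.5 SD, no dropout, and baseline-to-follow-up latent correlation r of 0.2, 0.3, 0.5 or 0.7.

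**Step 1: closed form, normal scores, t-type tests.** Power ≈ Φ(0.5·√(64/2)/s − 1.96) = Φ(2.828/s − 1.96), where s = 1 for the raw score, √(2(1−r)) for change and √(1−r²) for baseline-adjusted ANCOVA.

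- Raw: Φ(0.868) = 80.7% at any r.
- Change: 60.9 / 66.7 / 80.7 / 95.5%.
- ANCOVA: 82.3 / 84.3 / 90.4 / 97.7%.

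Change beats raw only when r exceeds 0.5. ANCOVA beats both at each of these correlations.

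**Step 2: simulation of rank tests.** 10,000 trials per setting. Baseline and follow-up are latent bivariate normal with correlation r, and 0.5 is added to one arm at follow-up. Three score shapes were used: normal; skewed (minus exp(−latent)); and ceiling (latent capped at 0.5, about 31% of controls at the cap). Rank ANCOVA regresses the ranks of the follow-up score on arm and the ranks of the baseline score. Power in % at r = 0.2 / 0.3 / 0.5 / 0.7:

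| Scores | Raw Mann-Whitney | Change Mann-Whitney, if between arms | Linear ANCOVA | Rank ANCOVA |
|---|---|---|---|---|
| Normal | 78.0 / 78.5 / 77.5 / 78.2 | 57.2 / 63.3 / 77.2 / 94.4 | 81.6 / 83.3 / 89.1 / 97.6 | 79.4 / 81.2 / 86.9 / 96.3 |
| Skewed | 78.8 / 78.1 / 78.6 / 78.1 | 45.1 / 50.1 / 64.1 / 82.3 | 61.7 / 62.3 / 68.5 / 79.5 | 79.9 / 80.9 / 87.9 / 96.1 |
| Ceiling | 73.3 / 73.2 / 73.2 / 73.5 | 44.6 / 48.3 / 58.5 / 78.6 | 71.8 / 73.4 / 80.0 / 91.4 | 74.6 / 76.5 / 81.4 / 92.1 |

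Gain of rank ANCOVA over raw Mann-Whitney, in points:

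- Normal: 1.4 / 2.7 / 9.4 / 18.1
- Skewed: 1.1 / 2.8 / 9.3 / 18.0
- Ceiling: 1.3 / 3.3 / 8.2 / 18.6

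Its type I error was 4.7-5.1%. A repeat with 8,000 trials per setting agreed to within about 2 points. Linear ANCOVA is not a safe substitute: with skewed scores it falls below the raw test up to r = 0.5.

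**Step 3: adding levels fused.** Assumed 32/22/10 patients per arm with 2, 3 and 4 levels, and 0.2 SD worse per level (4,000 trials). Raw Mann-Whitney against rank ANCOVA at r = 0.2 and 0.5 gave 77 v 80 and 78 v 88 (normal), 76 v 78 and 78 v 88 (skewed), 75 v 76 and 74 v 84 (ceiling). Type I error was 4.4-5.3%.

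**Step 4: the gain as sample size.** Raw-equivalent N = 128/(1−r_s²), with r_s = (6/π)·asin(r/2). At r = 0.5, r_s = 0.483 and N = 128/0.767 = 167. Across the four correlations N is 133 / 140 / 167 / 240 (normal approximation).

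**Step 5: chance imbalance.** The standard error of the baseline difference is √(2/64) = 0.177 SD. An imbalance of that size moves the raw difference by r × 0.177 = 0.04 to 0.12 SD over r = 0.2 to 0.7. It moves the change difference the other way by (1−r) × 0.177 = 0.14 to 0.05 SD.

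**Step 6: two undeclared tests.** If raw and change scores were both tested between arms at 0.05 and either could count, the simulated false-positive rate at one visit is 9.0 / 9.1 / 8.9% at r = 0.3 / 0.5 / 0.7 (normal scores, 4,000 trials).

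**The case against.** The Mann-Whitney test is a standard and valid choice for bounded questionnaire scores, so no error of inference is shown. That is right: the point concerns efficiency and clarity.

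The gain depends on a correlation the document does not give, and it could be low on days 1 and 2. The simulations above also give baseline and follow-up the same shape. Since the Background describes swallowing difficulty as a side effect of the surgery, pre-operative scores could cluster at the top of the scale. With 80% of baseline scores at the ceiling (an assumption; 4,000 trials), raw Mann-Whitney against rank ANCOVA at r = 0.2 / 0.3 / 0.5 was 77.5 v 78.2, 77.8 v 79.0 and 78.2 v 83.1% without a follow-up ceiling. It was 73.7 v 74.5, 72.8 v 73.9 and 73.4 v 78.2% with one. The gain shrinks to about 1 point at 0.2-0.3 and 5 at 0.5. This stands as a limit on size, and the raw-equivalent sample sizes shrink with it. The direction is unchanged, and at zero correlation adjustment did no material harm.

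The change-score power figures matter only if change is compared between arms. If it is descriptive, no power is lost through it. That also stands, and the plan's silence is why the role must be stated.

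The Outcomes section already promises stratification by levels, so the Statistical Plan's silence is partly a cross-reference gap. The Randomization section does not define procedure as number of levels, so the case for including levels rests mainly on Outcomes.

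Finally, no primary visit is named, and baseline adjustment does not cure that. It can still be applied at each post-operative visit the plan tests.

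**Conclusion.** The concern holds. The only between-arm test named for the primary measure ignores the baseline score, and the one analysis that uses baseline has no stated test, contrast or role. That omission is certain from the text; its size is not.

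Under 64 per arm and a 0.5 SD shift, rank-based adjustment adds about 1, 3, 8-9 and 18-19 points of power at correlations 0.2, 0.3, 0.5 and 0.7. With a heavy pre-operative ceiling it adds about 1-2 points at 0.2-0.3 and 4-5 at 0.5. It lost no power against the raw test in any of the 12 main settings, and type I error stayed near 5%. The planned comparisons are not biased. This is a change that should be made because it is nearly free, not because the design fails without it.

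**What to change.** 1. Make the deciding between-arm SWAL-QOL analysis a rank-based ANCOVA: ranks of the post-operative score on arm, ranks of the pre-operative score, and levels fused as three categories (2, 3, 4).
2. Report with it a baseline-adjusted difference and a bootstrap 95% confidence interval. The interval and the rank test address different quantities and can disagree, so state in advance that the rank test decides.
3. Keep the raw Mann-Whitney test as a sensitivity analysis.
4. Label the change score descriptive or supportive. If it is tested, name the between-arm test.
5. The Statistical Plan is written in the past tense. If outcomes have already been analysed, label the adjusted analysis as added afterwards.

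The cost is SAP wording and slightly more programming. It needs no new data and no more patients.
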